7.6.2 Laboratory Assessment

- Serum and plasma collection for banking
- Fasting lipid panel, glucose, and insulin level
- Hemoglobin A1c
- Serum 25-(OH) vitamin D level
- Serum PSA

7.7 End of Month 12 Study Visit (+/- 2 weeks)

7.7.1 Clinical Assessment

- Physical exam
- Concomitant medications
- ECOG Performance Status
- Quality of life questionnaires
 - SF-12, EPIC-26, HFRDIS, Lee Fatigue Scale, PHQ-9, Attentional Functional Index, empathy scale
- Weight, body mass index, and percent body fat by bioimpedance measurement

7.7.2 Laboratory Assessment

- Serum and plasma for banking
- Fasting lipid panel, glucose, and insulin levels
- Hemoglobin A1c
- Serum 25-(OH) vitamin D levels
- Serum PSA
- Serum testosterone

7.7.3 Radiographic Assessment

- DXA Scan
- High resolution peripheral quantitative CT scan of the distal tibia and radius (optional)

7.8 Concomitant Medications

Concomitant medications will be recorded at each study visit. The addition of medications to manage fasting blood glucose, lipids, bone density, or blood pressure will be allowed and at the discretion of the individual treating physician.

7.9 Follow Up

Patients randomized to the standard-of-care study arm will have the option of crossing-over to participation in the STAND clinic at the end of month 12 study visit. Patients who opt to participate in the STAND clinic will be followed for an additional 12 months. The STAND clinic schedule will be identical to that followed by patients initially randomized to the STAND clinic.

Following completion of STAND clinic participation, patients will be followed by telephone visit after 2 and 4 months to assess adherence to recommended diet/exercise plans. At 6 months following completion of the STAND clinic, patients will return for clinic assessment, which will include a physical exam, a measurement of weight, body mass index, percentage body fat, laboratory tests including evaluation of fasting glucose/lipid/insulin panels, hemoglobin A1c, plasma metabolites, serum PSA, serum testosterone and completion of quality of life questionnaires as outlined in the Appendix, and serum and plasma banking.

7.10 Duration of Study

The total duration of the study including follow up is expected to be approximately 5 years from the date the first patient is enrolled onto study.

8. Assessment of Study Variables

8.1 Percent Body Fat Estimation

Percent body fat will be estimated at baseline and every 3 months with the use of standard bioelectrical impedance monitor (see Appendix 4). Prior studies have demonstrated high reliability and strong correlation with other modalities including DXA scans.

8.2 Patient-Reported Outcomes

At baseline and every 3 months patients will complete quality of life and other questionnaires as outlined in Appendix 2. Patients will complete the questionnaires online within one week of study visit or at the time of study visit, either electronically or on paper. The PHQ-9 questionnaire must be completed on paper during the study visit. It is mandatory that the responsible health care provider for the study visit review and sign the results of the PHQ-9 prior to patient discharge from clinic.

8.3 Germline Polymorphisms

Collection of peripheral blood mononuclear cells for assessment of germline polymorphisms and their association with the relevant toxicities of ADT is an exploratory objective of the current study and patient participation in this aspect of the study is optional.

The genetic polymorphisms selected for this study were based on a literature review of prior studies which demonstrated significant associations between polymorphisms near or within select genes of interest encoding proteins involved in steroid hormone metabolism, intra-cellular transport, estrogen/androgen receptor signaling, and the IGF pathway with clinical outcomes on androgen deprivation therapy. Most prior studies included polymorphisms with a minor allele frequency > 5% in the CEU (Caucasian) population. The full set of polymorphisms to be analyzed is listed in Appendix 1.

Genomic DNA will be prepared from peripheral blood using a QIAamp DNA Blood Mini Kit (Quiagen Inc, Valencia, CA, USA). DNA will be stored at 4°C. Genotyping will be carried out using Sequenom iPLEX matrix-assisted laser desorption/ionization (MALDI)-time of flight mass spectrometry technology (Carlsbad, CA; http://www.sequenom.com/seq_genotyping.html/). Assays will be designed using Sequenom's MassARRAY AssignDesigner application, version 3.0. Polymerase chain reaction (PCR) and single base extension (SBE) oligonucleotides will be synthesized by Integrated DNA Technologies (Coralville, IA). PCR amplification will be performed using an input of 10 ng of DNA in a final volume of 6 L. The PCR products will be subsequently treated with shrimp alkaline phosphatase, and the SBE reactions will be initiated using iPLEX enzyme and mass-modified terminators (both Sequenom). After desalting, 7 nL of the SBE reaction will be spotted onto a SpectroCHIP (Sequenom) preloaded with 7 nL of 3-

hydroxypicolinic acid matrix. The SpectroCHIPs will be analyzed in automated mode by a MassArray Compact solid phase laser mass spectrometer system (Bruker Daltonics, Billerica, MA). The resulting spectra will be analyzed and genotypes called in real-time by the SpectroCaller algorithm, followed by additional user-initiated analysis with the SpectroTyper v.3.4A (Sequenom). The error rate on this platform is estimated to be less than 0.03%.

For the microsatellite analysis, DNA samples will be whole genome amplified using Illustra GenomiPhi V2 according to the manufacturer's recommended protocol (GE Healthcare, Chalfont St Gilles, UK). They will then be quantified using RNaseP Gene Expression Assay according to the manufacturer's recommended protocol (Applied Biosystems, Foster City, CA, USA). Polymerase chain reaction (PCR) will be performed using 2 μ M final concentration for both forward and reverse primers, 1.5 mmol/L Mg, and 0.2 units of Platinum Taq DNA Polymerase (Invitrogen, Carlsbad, CA, USA) in a final volume of 10 μ L. After an initial denaturation of 5 min at 94°C, samples will be through 35 cycles after 94°C for 40 s, the proper annealing temperature for 30 s, and 72°C for 30 s, followed by a final extension step of 72°C for 10 min. One microlitre of PCR product will be added to a mixture of Hi-Di Formamide (Applied Biosystems) and ROX400HD Standard (Applied Biosystems). Samples will then be denatured for 5 min at 95°C and placed on ice for 3 min, followed by capillary electrophoresis on an ABI 3730XL(Applied Biosystems). Genotypes will be scored using GeneMapper 4.0 (Applied Biosystems).

8.4 High Resolution Peripheral Quantitative CT Imaging

The image collection will take place at the China Basin imaging facility at UCSF. 3D trabecular bone density and structure, cortical bone density, thickness and porosity at the distal radius and tibia will be measured using high-resolution peripheral quantitative computed tomography (HRpQCT).

Regional of Interest Definition

In the superior-inferior direction we will collect 18 mm of image data, we will analyze this stack in two stages, the distal 9 mm, then 9 mm-18 mm. In addition regional analysis for trabecular bone, in 8 regions will be performed. The trabecular compartment will be divided into two concentric regions (inner and outer sub-regions), where the area of the inner sub-region will be 60% of the entire trabecular region. The volume will be further divided into axial quadrants. In the leg, a line connecting the axial centroids of the tibia and fibula and its orthogonal complement will define approximately medial-lateral/anterior-posterior quadrants. In the forearm, the major and minor axes of the axial cross section of the radius will define the medial-lateral/anterior-posterior quadrants. Each sub-region denoted by a two letter acronym based on location: I or O for inner or outer sub-regions, respectively; and M, P, L, or A for medial, posterior, lateral and anterior, respectively. Mean trabecular densitometric and micro-

architectural indices will be computed for each individual sub-region. The cortical analysis will be done in the 4 axial quadrants.

9. Planned Statistical Methods

9.1 Study Design

Randomized, phase 2 study with cross-over design to assess the longitudinal impact of participation in the multi-disciplinary STAND clinic vs. receipt of usual standard of care on changes in key metabolic parameters, quality of life, and patient satisfaction among men receiving androgen deprivation therapy for prostate cancer. Standard-of-care therapy will consist of every 3-month visits comprised of review of medical history, toxicity assessment, and lifestyle modification counseling provided by individual health care provider, LHRH analog injections by trained oncology nurse. Patients will have access to exercise, nutrition, and symptom management counseling if so requested by the patient or deemed necessary by health care provider. Men randomized to participation in the STAND clinic will receive, in addition to standard every 3 month visits with health care providers and LHRH analog injections, monthly self-directed educational “modules” covering the various aspects of hormone therapy as well as every 3-month individualized counseling provided by registered dietitian, exercise trainer, and symptom management service. At the end of 12 months of study participation, patients initially randomized to receive standard-of-care, will have the option of crossing-over to participate in the STAND clinic for the ensuing 12 months.

A non-randomized pilot cohort of 20 patients receiving concurrent chemohormonal therapy will be enrolled in parallel to assess the feasibility of STAND clinic participation in this patient population.

9.2 Determination of Sample Size and Study Power

The sample size estimate is based upon the primary endpoint of the study, the mean percent change in percentage body fat from baseline to 12 months. Based on prior prospective longitudinal studies, it is estimated that men receiving ADT and standard-of-care physician counseling regarding expected toxicities will experience a mean 12% (sd = 17%) increase in percentage body fat after 12 months of ADT [13]. If men participating in the STAND clinic, with individualized exercise/nutrition counseling and longitudinal assessment, have, on average, no increase in percentage body fat mass after 12 months of hormone therapy, this would warrant further evaluation of a multi-disciplinary clinic in a larger randomized clinical trial with long-term endpoints of interest, including incidence of diabetes and potentially cardiovascular disease. An enrollment target of 32 evaluable patients per arm will provide power of 80% to detect an effect size of 0.71 in the difference in mean percent change from baseline to 12 months in percentage body fat mass between the two arms, using a two-sample t test and a two-tailed level of significance = 0.05. The total planned accrual is 40 patients per arm accounting for an inevaluable rate of 20%.

A sample size of 20 patients is chosen for the non-randomized chemohormonal cohort to establish the feasibility of a multi-disciplinary clinic in this patient population. The primary endpoint for this pilot cohort is the percentage of completed STAND clinic visits, with a target goal of 80%. A sample size of 20 patients (13 visits per patient; 260 visits in total) provides 17.5% precision to determine the percentage of completed visits at 95% confidence.

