1.2 Rationale for the Clinical Study Endpoints

1.2.1 Rationale for the Primary Endpoint

The primary endpoint of the current study will be the mean percent change from baseline to 12 months in percentage body fat mass as calculated by bioelectrical impedance analyzer. Prior longitudinal studies have demonstrated a consistent mean percentage increase in percentage fat mass of 11-12% (+/- 1.5%) after 1 year of androgen deprivation therapy [13]. Cross-sectional imaging studies have shown a strong correlation with percentage body fat increases on ADT with increases in predominantly subcutaneous adipose tissue. Increases in body fat mass during ADT are strongly associated with other risk factors for diabetes and cardiovascular disease, including dyslipidemia, insulin resistance, and obesity. Results obtained via use of a bioelectrical impedance analyzer correlate with the use of other percent body fat assessments, including dual energy X-ray absorptiometry (DEXA) and underwater weighing methodologies, and intra-patient variability is low [14].

Measuring percentage body fat with handheld bioelectrical impedance device thus represents a readily obtainable, feasible, and clinically relevant marker of the metabolic impact of androgen deprivation therapy. It is hypothesized that comprehensive multi-disciplinary counseling may promote sustained lifestyle changes with respect to diet and exercise which may partially mitigate the adverse metabolic impact of ADT on percent body fat, and in turn, decrease the risk of longer term metabolic derangements including incidence of diabetes and cardiovascular morbidity and mortality.

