4.1 Inclusion Criteria

- Histologic confirmation of adenocarcinoma of the prostate
- Receiving or planning to receive ADT with LHRH agonist or antagonist
- Expected duration of ADT at least 12 months from date of study consent
- Concurrent antiandrogen therapy allowed but not required
- First dose of LHRH agonist or antagonist no more than 6 months prior to date of study consent
- Prior/concurrent radiation allowed
- Other investigational agents in addition to LHRH agonist/antagonist are allowed (e.g. novel anti-androgens, androgen synthesis inhibitors)
- Prior androgen deprivation therapy allowed, provided there is documented evidence of testosterone recovery to > 150 ng/dL and greater than 12 months duration between last “effective” date of ADT and date of study consent
- **Randomized cohort only:**
 - No prior chemotherapy within 12 months of start date of study
 - No planned chemotherapy at least 12 months from study entry
- **Non-randomized pilot cohort:**
 - Concurrent chemotherapy (initiated within 3 months of study entry) or planned chemotherapy within 3 months of study entry
- ECOG performance status of 0 – 2
- Ability to sign written informed consent
- Willing to attend monthly clinic visits at UCSF

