9.8.1 Analytic Plan for the Primary Objective

Two-sample t-test will be used to compare the mean percent change from baseline in percentage body fat after 12 months of study participation. The changes in percentage body fat across the

different time points will be evaluated using repeated measures analysis of covariance. To further characterize the patterns over the time and investigate the effect of treatment arm assignment, a linear mixed model will be applied with adjusting for stratification factors and covariates including Charlson co-morbidity index score, age, and baseline depression score as measured by PHQ-9. Patients who do not have a baseline or end-of-month 12 percentage body fat measurement, or those that start medications known to affect body fat/body weight during the course of the 12-month study, including metformin, insulin, corticosteroids, mirtazapine, or megestrol, will be excluded from the primary endpoint analysis. In an exploratory analysis, these patients will be retained to assess the impact of STAND clinic participation on changes in percentage body fat over time both before and after initiation of medical management.

For the non-randomized chemohormonal cohort, the point estimate and 95% confidence interval of the percentage of completed STAND clinic visits will be reported.

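### The 12% control-arm fat gain in 9.2 is counted from the start of ADT, but the endpoint is counted from study Day 1 after up to 6 months of ADT, so the stated 80% power may be too high

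*Combined protocol and SAP*

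**What the plan says.** **Assumed effect.** Section 9.2 assumes that men under usual care "will experience a mean 12% (sd = 17%) increase in percentage body fat after 12 months of ADT". Section 1.2.1 describes the same source as showing a "consistent mean percentage increase in percentage fat mass of 11-12% (+/- 1.5%) after 1 year of androgen deprivation therapy". Both count time on ADT. For the STAND arm, 9.2 assumes "on average, no increase in percentage body fat mass after 12 months of hormone therapy". It then states that 32 evaluable men per arm "will provide power of 80% to detect an effect size of 0.71", using a two-sided two-sample t test at 0.05.

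**Endpoint.** Section 9.2 defines it as "the mean percent change in percentage body fat from baseline to 12 months". Footnote f of the 7.1 schedule places the first bioimpedance reading on Day 1 of the study.

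**Entry.** Section 4.1 admits men planning ADT and men already on it: "First dose of LHRH agonist or antagonist no more than 6 months prior to date of study consent". The opening text of section 4 and the schema in the abstract set the same 6 months against Day 1 instead of consent. Section 7.3 stratifies on prior ADT, up to 3 months against 3-6 months.

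**Analysis.** Section 9.8.1 says: "Two-sample t-test will be used to compare the mean percent change from baseline in percentage body fat after 12 months of study participation". It also plans a linear mixed model for the pattern over time, adjusted for the stratification factors and other covariates.

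**The concern.** The planning value and the endpoint run on different clocks. A man who enters after 6 months of ADT is observed over months 6 to 18 of ADT. What he gained in months 0 to 6 is part of his baseline and cannot contribute to the difference between arms. Late entry is a planned part of the population, since 3-6 months of prior ADT is one of the two levels of a stratification factor. Yet 9.2 carries the full first-year figure forward without mentioning prior ADT.

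The trial is meant to show whether a larger trial is justified. If the control gain after baseline is smaller than 12%, a null result could reflect late entry and not an ineffective clinic, and a stated power of 80% would make that null look more conclusive than it is. Stratification balances prior ADT between the arms but does not restore a control-arm gain that came before baseline.

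**Working it through.** **Inputs from 9.2.** Control gain 12%, SD 17%, STAND change 0%, 32 evaluable per arm, two-sided alpha 0.05, two-sample t test.

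**Formula.** Power = P(|T| > c), where T is noncentral t with 2n − 2 = 62 degrees of freedom, noncentrality is (difference / SD) × √(n/2) = (difference / SD) × √16 = 4 × difference / SD, and c = 1.999.

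**Reproducing the plan**
- Effect size: 12/17 = 0.706, stated as 0.71.
- At 0.71: noncentrality 4 × 0.71 = 2.84, power 79.8%.
- At 12/17: noncentrality 2.82, power 79.4%.
- Enrolment: 32 / (1 − 0.20) = 40 per arm, as stated.

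The stated figures reproduce. Exactly 80% at SD 17 needs a difference of 12.1, so there is no slack.

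**Power when the control gain after study baseline is smaller** (STAND change 0, 32 per arm)

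| Control gain after Day 1 | SD | Effect size | Power |
|---|---|---|---|
| 12% | 17 | 0.706 | 79% |
| 10.5% | 17 | 0.618 | 68% |
| 9% | 17 | 0.529 | 55% |
| 6.5% | 17 | 0.382 | about 32% |
| 9% | 14 | 0.643 | 72% |
| 9% | 12.75 | 0.706 | 79% |
| 10.5% | 15 | 0.700 | 79% |

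The SDs below 17 are assumed values. They show how much a smaller spread would offset.

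**Where such gains could come from.** The documents give neither the gain curve nor the entry mix, so these are illustrations. Let f(t) be the mean gain after t months of ADT, with f(12) = 12. A man entering at month m has f(m + 12) − f(m) left.
- Gain linear throughout: 12 is left for every m.
- Gain linear to month 12, then flat: 12 − m is left. With entry uniform over 0-6 months the mean of m is 3, leaving 9.
- The same curve with half the men ADT-naive at Day 1 and half entering uniformly over 0-6 months: (12 + 9)/2 = 10.5.
- Gain saturating with a 3-month half-life: 12 × 2^(−m/3) is left. Averaged over 0-6 months this is 12 × 0.75 / (2 × ln 2) = 6.5.

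These subtract on the original scale. Re-expressing the gain relative to the raised baseline lowers it slightly: for m = 3 on the linear-then-flat curve, 1.12/1.03 − 1 = 8.7%, with power 53% in place of 55%.

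**The case against.** **The size cannot be derived from the documents.** This stands. The curves, half-lives and uniform entry are assumptions. Men not yet on ADT are eligible, so entry spread evenly over 0-6 months may overstate prior exposure. The 32% figure is a corner of the range.

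**The SD may not stay at 17.** This also stands. Effect size is difference over SD, and change over a later window may vary less. A reader might infer that 80% power holds only if every man enters at ADT start or the gain stays linear. That is too strong: a gain of 9% with SD 12.75 gives the same power as the plan's own inputs. A STAND mean below zero would also enlarge the difference, while one above zero would shrink it; 9.2 assumes exactly zero.

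**The statement in 9.2 is correct as written.** It claims power for an effect size of 0.71, and that claim is right. What is in doubt is whether 0.71 suits the men whom 4.1 admits.

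**Prior ADT is already in the analysis.** Partly so. The mixed model in 9.8.1 adjusts for the stratification factors, so it would be wrong to say that the plan ignores ADT duration. But 9.8.1 gives that model the role of describing patterns further, and the test that is named and powered for the primary comparison is the unadjusted t test.

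**Baseline could fall at about 7.5 months of ADT.** A reader might infer this by adding the 6 weeks that 7.2 allows between consent and Day 1 to the 6 months in 4.1. It follows only from the 4.1 wording. Section 4 and the schema count to Day 1, and the strata stop at 6 months.

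**Conclusion.** The mismatch of clocks is plain in the text, and 9.2 makes no allowance for it. With power at 79.4% for the full 12-point difference, any smaller control gain at SD 17 takes power below the stated 80%: 68% at 10.5%, 55% at 9%, about 32% at 6.5%. These figures assume 32 evaluable men per arm, SD 17 and no change on STAND. They are a range, not an estimate. At one end there is no loss, if the gain continues at the same rate beyond a year or nearly all men enter at ADT start. A smaller SD would recover part of the loss (72% at 9% with SD 14).

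The documents do not support the stronger conclusion that the trial is underpowered. They support the narrower one that the single figure of 80% depends on an unstated assumption about fat gain after study baseline, and that it may be too high.

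**What to change.** 1. **Section 9.2.** State the expected mix of prior ADT at Day 1 and the control gain assumed from study baseline for that mix. Replace the single 80% with power over a range of gain and SD, such as the table above.
2. **Section 9.8.1.** Keep percent change in percentage body fat as the primary outcome, so that the endpoint and the scale of the 12% and 17% are unchanged. Make the primary comparison an ANCOVA of that outcome adjusted for baseline percentage body fat and both stratification factors. The planned mixed model already carries the stratification factors. This should improve precision, but it does not recover gain lost before baseline.
3. **Reporting.** Give the effect by ADT-duration stratum descriptively. Each stratum holds only part of 32 men per arm, so no stratum test is warranted.
4. **Entry limit.** Reconcile section 4 and the abstract schema, which count the 6 months to Day 1, with 4.1, which counts them to consent.

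The cost is revised wording in 9.2 and 9.8.1, one reconciled eligibility statement and a less favourable stated power. No extra patients or assessments are needed.
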